Funding: No funding to report as of now. Funding by The Research Council of Norway is proposed after evaluation the developed prototype mentioned in this article.

Correspondence concerning this article should be addressed to [name]

IIIT Delhi University, [name].

Email: [contact]

ABSTRACT

Background: To take the existing VR technology to the next level, we developed a novel Intelligent Virtual Reality Therapy System (IVRTS). Aim: The objective of this project had three aspects: Namely, development of the novel IVRTS technology involving the development of a hardware device, development of Artificially Intelligent Psychotherapeutic software-interface and testing it's clinical efficacy. *Methods*: It used a two-phased methodology; Development of the novel technology and testing its Clinical Efficacy. After development of Novel IVRTS. A 7-week intervention was designed for each subject. The sample of 500 patients, meeting the criteria of Acrophobia and Anxiety, underwent the interventions at The GTB hospital (The University of Delhi), for a total 3500 sessions, ranging 5250 hours for over 2 years. The subjects were randomly divided into 4 groups: IVRTS Group, Mindfulness group, CBT group and Control Group. *Registration:* The ethics committee and clinical trial registration number is 3/1/333011/HRD. *Results*: The IVRTS group reported significant reduction in Acrophobic and Anxiety symptoms. The Pre and Post intervention, mean and SD reduced from 28.60±8.45 to 11.10±4.03 on HAMA; from 8.10±1.56 to 3.73±1.23 on SUDS and increased from 72.87±6.21 to 87.07±3.79 on WHO-QOL-BREF. It was also seen the mean comparison of reduction was significantly higher compared to the CBT and Mindfulness Groups. It also indicated enhanced Quality of Life (p < .001) compared to The Mindfulness Group and CBT Group. *Conclusion:* IVRTS decreased symptoms of Acrophobia and Anxiety, enhanced Quality of Life significantly than other treatment groups. Development of this technology is a land-mark innovation.

Key Words: Anxiety; Virtual Reality; Phobias; Treatment Intervention.

INTRODUCTION

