Furthermore, the main components of this project included –Hardware, software, system interfaces and data. The data being collected by the wireless sensor contains information about the health status of the user is stored in a database. Health status data included information about blood pressure, heart rate and other physiological parameters as well.

This project is aimed to develop both hardware and software technology and finally test its clinical efficacy to treat Phobias, General Anxiety, Stress and PTSD.

According to the DSM 5 published by the American Psychiatry Association¹⁴, specific phobias are associated with fear or Anxiety attached to a specific situation or Object Like water, animals, animals, public speaking, needles, heights, blood etc. DSM Also defines Generalized anxiety disorder (GAD) as a condition in which a person Feels intrusive, excessive, and persistent worrying to the extent that daily functioning becomes difficult.

Anxiety and Stress is becoming a global epidemic, The World Health Organization¹⁵, estimates that 1 in 3 from Clinical Anxiety and 1 in 5 individuals are suffering from Clinical Depression. About 80% of the world is suffering from general stress.

It is said that situation improves with pumping in of resources and putting in efforts; but in this situation despite putting in huge funds, highest quality of resources, the best human minds and fierce efforts, the problem is only increasing. The development of this novel technology will be a landmark step towards the intervention of these conditions the world is battling in present times.

Existing Work in VR

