In this health-related research, the researchers first applied to health research ethics committees for permissions and once the permissions are taken, then the researchers identified the sample or user groups, through seminars at the Gjøvik hospital, using social media, etc. The researchers made sure that the user consent is received, the participation in our studies are voluntary and their participation can be ended any time by the user without any penalties for the user. Also, the Clinical Trials took place at The Psychiatry OPD of the Guru Tegh Bahadur Hospital of The University of Delhi.

Figure 4: The software detects the pupil, after detection it determines the focus point of gaze to control the virtual interaction

Hypothesis:

- (i) The new novel developed technology Intelligent Virtual Reality Therapy System (IVRTS) is more effective in reducing symptoms of Phobia and Anxiety as compared to Mindfulness Meditation and Cognitive Behavior Therapy Groups.
- (ii) The novel IVRTS Group scores significantly lower on both Hamilton Anxiety Inventory (HAM-A) and Subjective Units of Dysfunction Scale (SUDS) compared to all three, The Control Group, The Mindfulness Group Cognitive Behavior Therapy (CBT) Group.
- (iii) The Novel IVRTS Group scores significantly higher on WHO Quality of Life Scale (WHO QOL BREF) compared to all three, The Control Group, The Mindfulness Meditation Group and The CBT Group.
- (iv) The new technology proves to be effective and a steppingstone towards a newer era in the treatment of Mental Health issues using Mental healthcare engineering.

Sample

The Clinical Trials were carried out on 500 adults with Acrophobia which is fear of heights co-morbid with Generalized Anxiety. The sample for the study was recruited from the patients/subjects attending the adult psychiatric OPD of the department of Psychiatry GTB Hospital of The University of Delhi and fulfilling the

ICD-10 diagnostic criteria for assessment of Acrophobia and generalized anxiety. The study was conducted on an initial 500 subjects attending the psychiatric OPD of the department of Psychiatry GTB Hospital of the University of Delhi. The subjects were equally and randomly assigned to three groups namely; Novel Intelligent Virtual Reality System (IVRTS) Group (n=125), Mindfulness Meditation Group (n=125), Cognitive Behavior Therapy (CBT) Group (n=125) and The Control Group (n=125).

[figure not shown]

Figure 5: Consort Diagram

Inclusion Criteria

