The Inclusion criteria included patients visiting the Psychiatry OPD of University College of Medical Sciences of the University of Delhi and the attached GTB Hospital.

Furthermore, those patients were selected who reported fear of heights and scored mild, moderate and Severe anxiety as assessed on Hamilton Anxiety Inventory. The patients were in the age group between 18 to 60 years of age.

Exclusion Criteria

Patients who had any Psychotic disorder or symptoms co-morbid were not selected for the study. Furthermore, patients below 18 years of age and aver 60 years of age were also not selected for the program

Registration

All procedures involving human subjects/patients were jointly approved by The University College of Medical Sciences (University of Delhi) and Delhi Psychiatry Society Ethics Committee registration. Registration number 3/1/333011/HRD. The patients were first recruited on 5th February 2018 for the project.

Procedure and Approaches

To achieve the stated objective, a two-fold approach comprising of qualitative and quantitative analysis was undertaken. A 7-week intervention course was designed for each subject to reduce symptoms and enhance quality of life as well as to establish clinical efficacy. The intervention was conducted on a sample of 500 patients diagnosed with Acrophobia co-morbid with generalized anxiety who underwent the intervention at The GTB hospital of The University of Delhi, for a total of 3500 sessions, ranging up to 5250 Hours over a period of 2 years. Written informed consent was obtained from all participants. The authors assert that all procedures contributing to this work comply with the ethical standards of the relevant national and institutional committees on human experimentation and with the Helsinki Declaration of 1975, as revised in 2008. All procedures involving human subjects/patients were jointly approved by The University College of Medical Sciences (University of Delhi) and Delhi Psychiatry Society Ethics Committee registration. Registration number 3/1/333011/HRD. Further study carried out A-B-A research design which mainly involved establishing a baseline condition, introducing an experimental treatment and then returning to the baseline. The subjects

completed standardized self-report measures of Hamilton Anxiety Inventory (HAM-A),
Subjective Units of Dysfunction (SUDS) and WHO Quality of Life - BREF Questionnaire

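### The abstract reports reduced acrophobia, but no reported outcome is stated to measure fear of heights, and what SUDS was rated against is not given

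*Combined protocol and SAP*

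**What the plan says.** The abstract makes the claim twice. Its Results say "The IVRTS group reported significant reduction in Acrophobic and Anxiety symptoms", followed by the IVRTS arm's pre and post figures on HAMA, SUDS and WHOQOL-BREF. Its Conclusion says "IVRTS decreased symptoms of Acrophobia and Anxiety, enhanced Quality of Life significantly than other treatment groups".

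In the Hypothesis section, hypothesis (i) is that IVRTS "is more effective in reducing symptoms of Phobia and Anxiety as compared to Mindfulness Meditation and Cognitive Behavior Therapy Groups"; no scale is attached. Hypothesis (ii) is that the IVRTS group "scores significantly lower on both Hamilton Anxiety Inventory (HAM-A) and Subjective Units of Dysfunction Scale (SUDS) compared to all three" comparison groups.

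Fear of heights appears as an entry condition. Under Sample, patients had to meet "ICD-10 diagnostic criteria for assessment of Acrophobia and generalized anxiety". Under Inclusion Criteria, "those patients were selected who reported fear of heights and scored mild, moderate and Severe anxiety as assessed on Hamilton Anxiety Inventory".

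For outcomes, Procedure and Approaches says that subjects "completed standardized self-report measures of Hamilton Anxiety Inventory (HAM-A"), together with SUDS and WHOQOL-BREF, at baseline, and that the same scales were repeated after seven sessions. The tables in Outcomes and Results report these three scales and no others.

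**The concern.** The abstract lists acrophobia beside anxiety as something that was reduced, so a reader will take it as a separate, demonstrated result. That needs an outcome that measures fear of heights after treatment as well as before. The readable text names none.

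Acrophobia is an entry diagnosis, phobia is in the stated objective, and phobia comes first in hypothesis (i). If the claim stands as worded, the trial will be cited as evidence that the system treats fear of heights, when the outcomes may show only that general anxiety and distress fell.

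**Working it through.** There is no planned figure to reproduce. The check sets the claim beside each outcome in the readable text.

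**1. What an acrophobia outcome has to capture.** The introductory section on the rationale for virtual reality says that "specific phobias are associated with fear or Anxiety attached to a specific situation or Object". It is a reasonable inference from that definition, though not a rule the document states, that a measure of change in acrophobia should be tied to heights.

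**2. Each candidate in turn.**

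| Measure | What the text ties it to | Stated to measure fear of heights? | Described before and after treatment? |
|---|---|---|---|
| HAM-A | Anxiety severity | No | Yes |
| SUDS | Subjective distress; rating target not given | No | Yes |
| WHOQOL-BREF | Quality of life | No | Yes |
| ICD-10 criteria | Acrophobia and generalized anxiety | Acrophobia diagnosis | Entry only |
| Patient-reported fear of heights | Fear of heights | Yes | Entry only |

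So 0 of the 3 outcomes is stated to be height-specific, and the two height-specific items are not described as repeated.

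**3. Whether HAM-A can stand in.** Sample and Procedure describe acrophobia as co-morbid with generalized anxiety, so the two are treated as distinct conditions. Inclusion Criteria list the HAM-A score separately from reported fear of heights. A fall in HAM-A therefore does not by itself show a fall in fear of heights.

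**4. Whether SUDS can stand in.** It could, if patients rated their distress about heights. The text does not say what situation, image or exposure was rated. All patients are described as also having generalized anxiety, so a fall in an unanchored SUDS could reflect relief of that anxiety. Exposure to the feared situation is described only for IVRTS, so a common height anchor across arms cannot be assumed.

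**5. What a claim resting on SUDS would use.** Mean falls from the printed tables:

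- IVRTS: 8.10 − 3.73 = 4.37
- Control: 8.27 − 6.03 = 2.24
- CBT: 8.24 − 5.34 = 2.90
- Mindfulness: 8.24 − 5.69 = 2.55

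The IVRTS fall exceeds these by 4.37 − 2.24 = 2.13 (control), 4.37 − 2.90 = 1.47 (CBT) and 4.37 − 2.55 = 1.82 (Mindfulness). These figures do not tell us whether SUDS measured fear of heights.

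**6. Which SUDS tests are printed.** Outcomes and Results says that paired t-tests were done, but no paired SUDS result for IVRTS is shown. Table 3 gives a SUDS test of IVRTS against control. Table 4 has no test statistics. The text after it gives one collective statement, a p-value below 0.01, for IVRTS against the other groups, not a SUDS result for each.

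**The case against.** The best reply is that hypothesis (ii) supplies the scales for hypothesis (i), and that the abstract follows its acrophobia sentence directly with the HAMA and SUDS figures. All patients were enrolled with acrophobia, so SUDS may well have been rated against heights. This stands as a possibility, and the fix allows for it. But neither place says that either scale measures fear of heights.

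A second reply is that the evidence may lie elsewhere. Several figures are not shown, and the text mentions qualitative analysis, biofeedback and fNIRS. The readable text reports no results from these, so the point is limited to the readable text.

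Three stronger readings are tempting but not supported:

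- **The verbal labels attached to SUDS scores show that it was not about heights.** They do not. They are words of intensity, and a height-anchored SUDS could carry the same ones.
- **The effectiveness statements in Outcomes and Results and in the Discussion make the same unsupported claim.** The first closes a paragraph giving the three scales by arm and refers back to those comparisons. The second is followed at once by a sentence naming anxiety and quality of life. The nearby description of a phobia treatment system is an aspiration.
- **Both abstract sentences fail unless all four arms used the same height stimulus.** The Results sentence is a within-group statement, so only the IVRTS arm's ratings bear on it.

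**Conclusion.** The abstract's acrophobia claim is not supported as reported. It affects two abstract sentences and the phobia part of hypothesis (i). The anxiety and quality-of-life conclusions have named scales and are not touched by this point.

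A reader might infer that acrophobia failed to improve, or that SUDS was certainly unrelated to heights. The documents support neither: the SUDS anchor is unreported, so whether SUDS supports the claim cannot be determined.

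The conclusion assumes that the missing figures contain no height-specific outcome and that no repeat of the entry assessment was made beyond what is described. This is more than a missing detail, because the answer decides what the trial may claim about its target phobia.

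**What to change.** State what SUDS was rated against, before and after treatment, in each arm. Then:

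- **Default.** Limit both abstract sentences to anxiety, subjective distress and quality of life. Report the phobia part of hypothesis (i) as not assessed by a phobia-specific measure.
- **If SUDS was rated against the same height stimulus before and after treatment in the IVRTS arm.** The within-group Results sentence may keep acrophobia, resting on SUDS alone, with the paired SUDS test reported.
- **If SUDS was so rated in every arm compared.** The between-arm claim in the Conclusion and in hypothesis (i) may also be kept, with the SUDS comparison of IVRTS against each of those arms reported.

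The default costs one line on how SUDS was rated, two reworded abstract sentences and one line on hypothesis (i). Keeping the claim costs more, because it needs scale-specific SUDS results that the readable text does not print. The downside for the sponsor is that the acrophobia claim may have to be narrowed or given up.

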According to Garcia Et al¹⁶, Virtual Reality has gained widespread acceptance in the field of psychiatry. Mainly pertaining to phobias within anxiety disorders, VR has been found to be useful in the treatment of phobia of spiders¹⁷, heights¹⁸, flying¹⁹ and claustrophobia²⁰, to name a few. As VR allows for the creation of images and scenarios, the subject can be taken back to the fearful or anxiety-provoking situation. The therapist can then guide and monitor the subjects' responses and thereby treat anxiety. Walshe and Lewis et al²¹ mentions in their research that VR has thus also been successfully utilized to treat phobia of driving in patients who have Post-Traumatic Stress Disorder (PTSD) after an accident. Also, Horváthová and Siládi ²² proved in their research how Virtual environments created by virtual reality (VR) tools can help to make the treatment of certain types of phobias more efficient. Further Keller and Bunnel eta al²³, using systematic literature search analyzed VR based treatments and emphasized on their benefits viz-a-viz psychiatric and Psychological research and intervention to overcome anxiety.

NOVELTY OF THE PROJECT

The approach of the Novel Intelligent Software interface approaches follows the basic premise that human beings think in terms of images rather than words. While the existing modes of treatment for phobias rely mainly on talk therapies and counseling; This novel intelligent software treatment methodology

deals with the development of VR programs integrated with hardware for simulating various phobia-inducing situations, followed by novel automated integrated most effective psychotherapy; altering these images to reduce the anxiety experienced. Our treatment package includes a VR device integrated with easily comprehensible voice commands, along with a user manual and easy user interface, thereby reducing the effort of training required for operating the device. The framework is a combination of the therapy methodologies with VR, motion sensors, biofeedback and fNIRS. This would eliminate the need for a therapist by making the patient self-sufficient in handling the overall treatment themselves. In the long run, this would prove to be more cost-effective and socially accessible.

METHODOLOGY Objective, Approaches, hypotheses and choice of method

[figure not shown]

Figure 1: Conceptualization of research and development of project

[figure not shown]

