Figure 2: Intelligent Interactive Psychotherapy Program Software (IIPPS)

Objective

To develop Novel Technology, Intelligent Virtual Reality Therapy System (IVRTS) and test its Clinical Efficacy to treat phobias and anxiety, compared to Mindfulness Meditation and Cognitive Behavior Therapy (Talk Therapy).

Concept

Virtual Reality has a vast potential in healthcare. One such area where VR is becoming a promising technique is the treatment of Phobias and Anxiety Disorders. There are various types of phobias, and amongst them, some occur more commonly in individuals, in general. In the treatment of phobia using VR, the patient re-enters a computer-generated environment that is the imitation of the situation or an object the patient possesses the fear of. It helps people to encounter situations or objects they fear while being in a completely safe and controlled environment. The environment is

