(QOL-BREF) at baseline, after seven intervention sessions post assessments on the same scales were repeated to assess the efficacy.

The Therapeutic Software of IVRTS

The researchers developed four different technological approaches to develop the Psychotherapeutic Software. (1) Since phobias are known to stem from mental images of situations or objects which an individual has learned to be fearful of. Thus, the most effective way to treat them, then, would be to alter these anxietyprovoking images with the help of graded exposure of an image of a situation or object which induces maximum pleasure and positive emotions within the individual. This was achieved with the help of development of motion sensors to detect the wrist movements of the subjects, which aided in achieving the desired goal of stimulating the pleasure-inducing stimulus to reduce anxiety. This was accompanied by monitoring the subject's physiological parameters through body biofeedback and fNIRS depicting the changes brought about by VR therapy and keeping the record of the same. (2) When an individual encountered a fearful stimulus, certain kind of neurotransmitters are released in the brain and over time, the body and mind of the individual learn to associate the release of these neurotransmitters with fear. This association was altered by flooding the individual's mind with pleasurable memories in the form of positive images using Virtual Reality Technology and thereby replacing unpleasant memories attached to the neurotransmitter release with pleasant memories. It was followed by guided instruction from the IVRTS device along the concept of 'Whole Brain Thinking' wherein all the five sense organs are used to exercise all the parts of the brain to take advantage of a wide spectrum of thinking. (3) As described in Figure 1, Cognitive Behavioral Therapy

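### No harm, tolerability or worsening outcome is defined or reported in any arm, and 36 of 500 randomised patients go unexplained in the text, so IVRTS is ranked above CBT and Mindfulness with no harm comparison

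*Combined protocol and SAP*

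**What the plan says.** **Outcomes.** Under Procedure and Approaches, subjects "completed standardized self-report measures of Hamilton Anxiety Inventory (HAM-A"), SUDS and WHOQOL-BREF at baseline; then "after seven intervention sessions post assessments on the same scales were repeated to assess the efficacy". The Abstract gives the length: "A 7-week intervention was designed for each subject". No later assessment is described. The four hypotheses all concern benefit.

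**Reporting.** Outcomes and Results gives arm means and SDs at both times, with t, F and p values for each comparison with Control. Table 4 sets the three active arms side by side. The text concludes that IVRTS is the most effective, ahead of CBT and Mindfulness.

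**Other data.** The Introduction, on the device's components, states: "Health status data included information about blood pressure, heart rate and other physiological parameters as well". The section on the therapeutic software adds monitoring of "physiological parameters through body biofeedback and fNIRS depicting the changes brought about by VR therapy and keeping the record of the same". Neither is named as a safety measure and neither is reported.

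**Safety and supervision wording.** The Concept section contains "It helps people to encounter situations or objects they fear while being in a completely safe and controlled environment". The sentence just before it sets the subject: "In the treatment of phobia using VR, the patient re-enters a computer-generated environment". Novelty of the Project says of the package: "This would eliminate the need for a therapist by making the patient self-sufficient in handling the overall treatment themselves". Discussion and Conclusion says the reverse, that the technology is meant to accompany human intervention and not to take its place.

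**Numbers.** The Sample section randomises 125 to each of four arms. The results tables analyse 115 (IVRTS), 118 (Mindfulness), 106 (CBT) and 125 (Control).

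**The concern.** IVRTS raises fear in steps, in patients whose mean baseline HAM-A the authors class as moderate to severe (IVRTS) or very severe (the other arms). The stated exclusions are psychotic disorder or symptoms, and age. A treatment of this kind can distress some patients while the arm mean improves, and a patient who stops because of distress does not contribute to a mean over those analysed.

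The trial ranks IVRTS above two established treatments and describes a future in which patients run it themselves. A reader choosing between IVRTS and CBT needs both sides of that comparison. The documents give the benefit side only. The limitations section discusses cross-cultural validity and does not mention harm.

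**Working it through.** The documents state no harm rate, so there is no figure to reproduce. Three checks apply.

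**1. Patients missing from the analysis.** Loss = 125 − analysed n.

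| Arm | Randomised | Analysed | Missing |
|---|---|---|---|
| IVRTS | 125 | 115 | 10 (8.0%) |
| Mindfulness | 125 | 118 | 7 (5.6%) |
| CBT | 125 | 106 | 19 (15.2%) |
| Control | 125 | 125 | 0 |
| Total | 500 | 464 | 36 (7.2%) |

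All 36 are in the active arms. For IVRTS against Control (10/125 against 0/125), Fisher's exact test gives p = 0.002. The IVRTS loss is smaller than the CBT loss.

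**2. How many patients could have worsened.** Take change scores as normal with mean d (the size of the mean improvement) and SD = √(s₁² + s₂² − 2·r·s₁·s₂), where s₁ and s₂ are the printed pre and post SDs. The share that worsened is Φ(−d/SD). The documents do not give r, so I use 0.5 to 0.8, with r = 0 as an extreme. I also take the printed pre and post figures to describe the same patients.

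- Control HAM-A: d = 33.70 − 28.00 = 5.70. At r = 0.5, SD = √(6.08² + 6.49² − 6.08×6.49) = 6.30, giving Φ(−0.905) = 18.3%. At r = 0.8, SD = 3.99, giving 7.7%.
- IVRTS HAM-A: d = 28.60 − 11.10 = 17.50. At r = 0.5, SD = √(8.45² + 4.03² − 8.45×4.03) = 7.32, giving Φ(−2.39) = 0.8%. At r = 0.8, SD = 5.76, giving 0.1%.

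The same formula for all arms:

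| Arm | HAM-A rose, r = 0.8 / 0.5 / 0 | QOL fell, r = 0.8 / 0.5 / 0 |
|---|---|---|
| IVRTS | 0.1 / 0.8 / 3.1% | 0.0 / 0.4 / 2.6% |
| Mindfulness | 0.0 / 0.5 / 3.2% | 1.5 / 6.7 / 13.6% |
| CBT | 0.0 / 0.9 / 4.5% | 0.2 / 3.0 / 9.2% |
| Control | 7.7 / 18.3 / 26.1% | 1.6 / 8.6 / 16.6% |

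The range within an arm is wide, so means and SDs cannot settle the counts; the individual scores can. In IVRTS the modelled HAM-A share is about 1 of 115 at r = 0.5 and 3 to 4 of 115 even at r = 0. That is smaller than the 10 patients not analysed.

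**3. What a recorded zero would have shown.** With no events in 115 patients, the exact upper limit is 1 − 0.05^(1/115) = 2.6% (one-sided 95%) or 1 − 0.025^(1/115) = 3.2% (two-sided 95%). This is hypothetical, since no count is reported. It shows that even a clean record would not establish complete safety.

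**The case against.** The strongest reply has five parts.

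- **Data were collected.** Scores were taken per patient, and all three scales can move in either direction. The device also stored physiological data. A reader might infer that only means were collected, or that patients who worsened cannot be found. The documents do not support either inference: worsening on the scales was measured but not tabulated. This stands, and it makes the remedy cheap.
- **The safety sentence is general.** A reader might take it as a finding about IVRTS. Its subject is VR phobia treatment, in a passage that contrasts simulation with taking a patient into the real situation. This stands. What remains is unqualified wording in the rationale for this device that the trial did not test.
- **Therapist-free use is an aspiration, and the Discussion contradicts it.** The trial itself ran in a hospital outpatient department. This stands as a reason to reconcile the two statements, not to treat unsupervised use as the settled plan.
- **The arithmetic favours IVRTS.** A reader might infer that many IVRTS patients deteriorated. The printed figures point the other way: among analysed patients, modelled IVRTS worsening is small and far below Control. Also, any rise counts as worsening in that model, so measurement error is included.
- **Reasons for loss may be in the CONSORT figure.** They may; only the readable text can be judged. A list of reasons would answer part of the point, but would not supply a harm outcome.

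None of this supplies a harm comparison between arms.

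**Conclusion.** The point holds as a gap in defining and reporting harm. No arm has an adverse-event, tolerability or deterioration outcome in the readable text, and 36 of 500 patients (7.2%), all in active arms, are unaccounted for there. The ranking of IVRTS above CBT and Mindfulness therefore concerns efficacy alone.

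The documents do not show that IVRTS harmed anyone or that losses were caused by harm. The unknowns that matter for IVRTS are the 10 unanalysed patients and effects outside the three scales, such as VR sickness or panic during exposure.

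The loss counts follow from printed numbers. The worsening percentages rest on assumed normality and an assumed correlation; they show why the real counts are needed and do not estimate them reliably. The sponsor should act on this, but it does not by itself overturn the efficacy results.

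**What to change.** 1. From the scores already held, report for each randomised arm the number and percentage whose HAM-A rose, whose SUDS rose, and whose QOL fell, with between-arm differences and 95% CIs. Show the number without a post score beside each count.
2. Report the reason for each of the 36 losses, by arm.
3. Tabulate by arm any adverse events found in clinic records, and report the stored physiological data for the arm or arms in which they were recorded. If nothing was recorded, state plainly that harms were not collected and limit the conclusion to efficacy.
4. Qualify the safety sentence in the Concept section as a general statement about VR that was not tested here. Reconcile the statements on the therapist's role in Novelty of the Project and in Discussion and Conclusion.
5. In any further enrolment, record adverse events and reasons for stopping with the same question in all arms, at visits that already take place. This cannot be added to completed sessions.

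Cost: item 1 is one table from existing data. Items 2 and 3 need a search of trial and clinic records. Item 4 is editing, and item 5 is a short form. The drawback is a little extra analysis and a possibly less favourable message.
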